8.5.2 Analysis of other endpoints

(1) Changes in mean Hb values from the first day of the treatment period at Weeks 48 and 52 of the treatment period

Descriptive statistics for change from Hb on the first day of the treatment period to mean Hb at Week 48 and Week 52 in the treatment period should be calculated by treatment group. A paired t-test should be performed for before and after comparison of changes from the first day of the treatment period.

A group comparison should be conducted for the change from the first day of the treatment period using the MMRM (with compound symmetry [CS] for a covariance matrix within subject variance). LSMean, its standard errors, and 2-sided 95% CI for change from Hb on the first day of the treatment period to mean Hb at Week 48 and Week 52 in the treatment period should be calculated by treatment group. The point estimate, its standard errors, 2-sided 95% CI, and p-value of the between-group difference (MT-6548 – darbepoetin) of LSMean should be calculated.

Only the Correction and Conversion (Hb < 11.0 g/dL) cohorts should be analyzed. The Conversion (Hb < 11.0 g/dL) cohort should be summarized in the MT-6548 group only.

(2) Proportion of subjects with a ≥ 1.0 g/dL increase in mean Hb values from the first day of the treatment period at each time point of the treatment period.

The number and proportion of subjects and 95% CI (Clopper-Pearson [exact] method) of the proportion of subjects with an Hb value increase of ≥ 1.0 g/dL from the first day to each evaluation time point of the treatment period should be provided.

The estimate, its 95% CI (exact method), and p-value (Fisher's exact test) for between-group difference (MT-6548 – darbepoetin) should be calculated for the proportion of subjects whose Hb level increased by ≥ 1.0 g/dL at each evaluation time point from the first day of the treatment period.

Only the Correction and Conversion (Hb < 11.0 g/dL) cohorts should be analyzed. The Conversion (Hb < 11.0 g/dL) cohort should be summarized in the MT-6548 group only.

(3) Number of days to maintain the target Hb values

The number of maintenance days should be calculated from reaching to leaving the target Hb range for each subject, and the descriptive statistics should be calculated. Only the MT-6548 group is analyzed. However, if treatment period is completed in 52 weeks, the maintenance days should be until Week 52 of the treatment period. No analysis will be performed for patient cohorts.

(4) Proportion of subjects receiving rescue therapy with ESA formulations, red blood cell transfusion, or phlebotomy

The number and proportion of subjects and the 95% CI (Clopper-Pearson [Exact] method) for the proportion of subjects receiving rescue therapy with an ESA preparation should be provided by treatment group, after the first day of the treatment period, in each period between scheduled study visits and during the entire treatment period from the first day to Week 52 of the treatment period.

The estimate, its 95% CI (exact method), and p-value (Fisher's exact test) for between-group difference (MT-6548 – darbepoetin) should be calculated for the proportion of subjects receiving rescue therapy.

The analyses same to the above subjects receiving rescue therapy with ESA formulation should be performed for subjects receiving rescue therapy with RBC transfusion or receiving phlebotomy.

(5) Study drug dosage

1) Study drug dosage

Descriptive statistics of the average daily dose of MT-6548 and mean weekly dose of darbepoetin alfa injection (recombinant) should be calculated, after the first day of the treatment period, in each period between scheduled study visits and during the entire treatment period from the first day to Week 52 of the treatment period. The time course diagram for mean daily dose of MT-6548 and mean weekly dose of darbepoetin alfa injection (recombinant) should be separately prepared by treatment group. 95% CI of the mean will be represented by an error bar. Each period between scheduled study visits is defined as the period between the scheduled visit and the day before the next scheduled visit.

2) Distribution of MT-6548 tablets and darbepoetin alfa injection

The number and proportion of subjects and the 95% CI (Clopper-Pearson [Exact] method) of proportion per daily dose of MT-6548 tablets and per weekly dose of darbepoetin alfa (recombinant) during the treatment period should be provided by treatment group.

The proportion of subjects receiving each dose of MT-6548 tablets and darbepoetin alfa injection (recombinant) at each evaluation time point of the treatment period should be provided as a stacked bar graph with the number of subjects in each treatment group as 100%. Stacked bar charts should be generated separately for each treatment group.

If no prescription is available on the day of each evaluation timepoint of the treatment period, the dose should be based on the immediately before prescription.

3) Analysis of timing of administration of MT-6548 tablets (before meal, after meal, other)

An analysis similar to “1) Study drug dosage” should be conducted according to the timing of administration of MT-6548 tablets (before meal, after meal, other). Only the MT-6548 group is analyzed. No analysis will be performed for patient cohorts.

4) Analysis by previous ESA formulation type

An analysis similar to “1) Study drug dosage” should be conducted by the type of previous ESA formulation (epoetin alfa or epoetin beta, darbepoetin alfa, epoetin beta pegol).

Conversion, Conversion ($Hb \geq 11.0 \text{ g/dL}$), and Conversion ($Hb < 11.0 \text{ g/dL}$) cohorts will be analyzed in the MT-6548 group only.

5) Analysis by dose of previous ESA formulation types

An analysis similar to “1) Study drug dosage” should be conducted for weekly dose (darbepoetin alfa, epoetin beta pegol: $\geq 15 \mu\text{g}$, $< 15 \mu\text{g}$) of previous ESA formulation by type (darbepoetin alfa, epoetin beta pegol). The number of patients classified by dose was set to be almost equal.

Conversion, Conversion ($Hb \geq 11.0 \text{ g/dL}$), and Conversion ($Hb < 11.0 \text{ g/dL}$) cohorts will be analyzed in the MT-6548 group only.

6) Analysis of Hb values on the first day of the treatment period

An analysis similar to “1) Study drug dosage” should be conducted for the Hb value on the first day of the treatment period (divided the number of subject into 3 categories at tertiles).

7) Analysis with or without iron supplements and iron-containing phosphate binders

An analysis similar to “1) Study drug dosage” should be conducted for subjects continuously using iron supplements or iron-containing phosphate binders and subjects never using iron supplements and iron-containing phosphate binders during the treatment period. Only the MT-6548 group is analyzed. However, subjects who uses intravenous iron at least once should be excluded from the tabulation. Since intravenous iron should be included in the tabulation for treatment period phase 1, the tabulation for treatment period phase 1 should be output again.

8) Analysis by iron supplements and iron-containing phosphate binders formulations

An analysis similar to “1) Study drug dosage” should be conducted for subjects using iron supplements or iron-containing phosphate binders continuously during the treatment period. Analysis should be performed only in the MT-6548 group, and no analysis will be performed for patient cohorts. However, subjects who use intravenous iron at least once should be excluded from the tabulation.

9) Analysis of the mean dose of the study drug at Week 48 to Week 52 of the treatment period and CRP values on the first day of the treatment period

For MT-6548 group only, a scatter plot chart should be provided after linear regression with the following variables. No analysis will be performed for patient cohorts.

x: Logarithmic CRP value on the first day of the treatment period

y: Study drug average dosage at Week 48 to Week 52 of the treatment period

(6) Total number of dosage adjustments

The number and proportion of subjects and the 95% CI (Clopper-Pearson [Exact] method) for the proportion of subjects receiving dose adjustment should be provided, after the first day of the treatment period, in each period between scheduled study visits and during the entire treatment period from the first day to Week 52 of the treatment period.

The number and proportion of subjects and the 95% CI (Clopper-Pearson [Exact] method) for the proportion of subjects should be provided for the proportion of subjects defined below in each period between scheduled study visits. If a subject is included in more than one definition, the subject should be counted in each definition.

No dose adjustment: No change

With dose adjustment: dose adjustment (Dose adjustment), dose increase (Increase), dose decrease (Decrease), drug interruption (Interrupt)

Dose adjustment (Dose adjustment) should include the number of times of increase, decrease, and interruption, and should not count the increase when it is resumed after interruption. Only the MT-6548 group will be tabulated.

(7) Iron supplement dosage

The following should be provided according to the 3 categories of oral iron supplement, intravenous iron supplement, and iron supplement (any route).

Descriptive statistics of the mean dose of iron supplement per month for each treatment group should be calculated for the screening period, and after the first day of the treatment period, in each period between scheduled study visits and during the entire treatment period from the first day to Week 52 of the treatment period.

Descriptive statistics of the change in the mean dose of iron supplement per month from the baseline (mean dose of iron during the screening period) should be calculated, after the first day of the treatment

period, in each period between scheduled study visits and during the entire treatment period from the first day to Week 52 of the treatment period. Before and after comparison should be conducted for changes from baseline using the paired t-test. The changes should be compared between groups using the Student-t test. The mean value of the between-group difference (MT-6548 – darbepoetin), its two-sided 95% CI, t-statistic, and p-value should be provided.

The dosage of iron supplement should be calculated using the dose as iron.

If no iron supplement is administered, the dose should be tabulated as 0 mg. Subjects who changed the administration route of an iron supplement during the treatment period and subjects who had never received an iron supplement during the treatment period should be excluded from the tabulation.

(8) Proportion of subjects receiving oral, intravenous, or (any route) administration of iron supplements

The number and proportion of subjects and the 95% CI (Clopper-Pearson [Exact] method) for the proportion of subjects treated with oral, intravenous, or oral iron supplement (any route) should be provided by treatment group for screening period, and after the first day of the treatment period, in each period between scheduled study visits and during the entire treatment period from the first day to Week 52 of the treatment period. McNemar tests should be used to compare baseline values (proportion of subjects receiving iron supplements by the aforementioned route in the screening period) with those before and after each period between scheduled study visits. The estimate, its 95% CI (exact method), and p-value (Fisher's exact test) for between-group difference (MT-6548 – darbepoetin) should be calculated for the proportion of subjects receiving oral, intravenous, or (any route) iron supplement.

Subjects who have not received an iron supplement are to be subjects who have never received an iron supplement during the relevant period, and subjects who have received an oral, intravenous, or (any route) iron supplement are to be subjects who have received an iron supplement at least once during the relevant period.

(9) Proportion of subjects with serum ferritin values of ≥ 100 ng/mL or TSAT of $\geq 20\%$.

The number and proportion of subjects and 95% CI (Clopper-Pearson [exact] method) of the proportion of subjects with serum ferritin values of ≥ 100 ng/mL or TSAT of $\geq 20\%$ should be provided at each evaluation time point of the treatment period for each treatment group. Before and after comparison should be conducted for changes between the first day of the treatment period and each period between scheduled study visits using the McNemar test. Changes in iron-related measures (serum iron, TIBC, TSAT, and serum ferritin) and hepcidin should be calculated from the first day of the treatment period to each evaluation time point of the treatment period.

(10) Changes and rate of changes in iron-related indices (serum iron, TIBC, TSAT, and serum ferritin values) and hepcidin from the first day of the treatment period

Changes in iron-related measures (serum iron, TIBC, TSAT, and serum ferritin) and hepcidin should be calculated from the first day of the treatment period to each evaluation time point of the treatment period. A paired t-test should be performed for before and after comparison of changes and change rates from the first day of the treatment period.

A group comparison should be conducted for the change in iron-related measures (serum iron, TIBC, TSAT, and serum ferritin) and hepcidin from the first day of the treatment period to each evaluation time point using the MMRM (with compound symmetry [CS] for a covariance matrix within subject variance). LSMean, its standard errors, and 2-sided 95% CI should be calculated, and the point estimate, its standard errors, 2-sided 95% CI, and p-value should be provided for the group difference (MT- 6548 – darbepoetin) of the LSMean by treatment group. Only the serum ferritin value at each evaluation time point of the treatment period should be similarly compared between groups.

The time course diagram of changes in the iron-related measures (serum iron, TIBC, TSAT, and serum ferritin values) and hepcidin from the first day of the treatment period to each evaluation time point should be prepared for each treatment group. The 95% CI of LSMean will be represented by an error bar. For only the serum ferritin value, a time course diagram should be prepared for mean ferritin values and 95% CI at each evaluation time point of the treatment period.

The serum ferritin values should be shown as follows.

An analysis similar to the above should be conducted for serum ferritin at baseline (divided the number of subject into 3 categories at tertiles). Time course diagram for mean and 95% CI should be prepared separately by treatment group.

The following scatter plot chart should be provided by treatment group. Linear regression should be performed to calculate the p-value and correlation coefficient of the test with zero slope as the null hypothesis.

x: Serum ferritin at baseline

y: Serum ferritin at Week 52 of the treatment period

(11) Change in hematocrit, red blood cell count, reticulocyte (count and rate), mean corpuscular volume, mean cell hemoglobin, and EPO (MT-6548 group only) from the first day of the treatment period

Descriptive statistics of hematocrit, red blood cell count, reticulocyte (count and rate), mean corpuscular volume, mean cell hemoglobin, and EPO (MT-6548 group only) at each evaluation time point should be calculated for each dose group. And, the change from the first day of the treatment period should be obtained, and the descriptive statistics should be calculated for each dose group. A

paired t-test should be performed for before and after comparison of changes from the first day of the treatment period.

A group comparison should be conducted for the change in hematocrit, red blood cell count, reticulocyte (number and rate), mean corpuscular volume, mean corpuscular hemoglobin, and EPO (MT-6548 group only) from the first day of the treatment period to each evaluation time point using the MMRM (with compound symmetry [CS] for a covariance matrix within subject variance). LSMean, its standard errors, and 2-sided 95% CI should be calculated, and the point estimate, its standard errors, 2-sided 95% CI, and p-value should be provided for the group difference (MT-6548 – darbepoetin) of the LSMean by treatment group. EPO will be analyzed in the MT-6548 group only. Hematocrit, RBC count, and reticulocytes (number and rate) in the Conversion (Hb < 11.0 g/dL) cohort should be analyzed only in the MT-6548 group. No statistical test should be conducted for hematocrit, RBC count, and reticulocytes (number and rate) in the Conversion cohort and Conversion (Hb \geq 11.0 g/dL) cohort for group differences and the difference between baseline and each evaluation time point in the treatment period for the darbepoetin alfa group.

A histogram of EPO measurements should be prepared for evaluation time point at Week 52 of the treatment period.

(12) Changes in systolic blood pressure, diastolic blood pressure, and blood glucose from the start of the treatment period, changes and the rate of change in lipid (total cholesterol, LDL-C, HDL-C, LDL-C/HDL-C ratio, triglycerides) from the start of the treatment period

Systolic blood pressure, diastolic blood pressure, lipids (total cholesterol, LDL-C, HDL-C, LDL-C/HDL-C ratio, triglycerides), and blood glucose should be analyzed in the same manner as hematocrit, red blood cell count, and reticulocyte (number and rate) in the preceding section.

Descriptive statistics for each measurement at the evaluation time point of Week 52 of the treatment period should be calculated by baseline value (divided the number of subject into 3 categories at tertiles). And, the change from the first day of the treatment period should be obtained, and the descriptive statistics should be calculated for each dose group. A paired t-test should be performed for before and after comparison of changes from the first day of the treatment period. A group comparison should be conducted for the change from the first day of the treatment period using the MMRM (with compound symmetry [CS] for a covariance matrix within subject variance). LSMean, its standard errors, and 2-sided 95% CI should be calculated, and the point estimate, its standard errors, 2-sided 95% CI, and p-value should be provided for the group difference (MT-6548 – darbepoetin) of the LSMean by treatment group.

The descriptive statistics should be similarly calculated for each administration group on the rate of change from the first day of the treatment period at each evaluation time point of the lipid (total cholesterol, LDL-C, HDL-C, LDL-C/HDL-C ratio, triglycerides), and a group comparison should be

conducted using the MMRM (with compound symmetry [CS] for a covariance matrix within subject variance).

No analysis will be performed for patient cohorts.

(13) Renal function-related measures (eGFR, serum creatinine, urinary albumin/creatinine ratio) should be analyzed in the same way as hematocrit, red blood cell count, and reticulocyte (count and rate) in the previous section.

Renal function-related measures (eGFR, serum creatinine, urinary albumin/creatinine ratio) should be analyzed in the same way as hematocrit, red blood cell count, and reticulocyte (count and rate) in the previous section.

Descriptive statistics for changes in eGFR and urinary albumin/creatinine ratio from the first day of the treatment period to each evaluation time point should be similarly calculated for each administration group, and a group comparison should be conducted using the MMRM (with compound symmetry [CS] for a covariance matrix within subject variance).

The following items should also be calculated.

- The number, proportion, and 95% CI (Clopper-Pearson [Exact] method) of subjects with a $\geq 30\%$ decrease in eGFR from the start of the treatment period during the evaluation time point of Week 52 of the treatment period should be provided for each treatment group.

The estimate, its 95% CI (exact method), and p-value (Fisher's exact test) for between-group difference (MT-6548 – darbepoetin) should be calculated for rate of subjects with a $\geq 30\%$ decrease in eGFR from the start of the treatment period at the evaluation time point of Week 52 of the treatment period.

- The same analysis as above should be performed for the number of subjects with an eGFR decrease of $\geq 40\%$ from the start of the treatment period at the evaluation time point of Week 52 of the treatment period.

- The same analysis as above should be conducted for the number of subjects with serum creatinine ≥ 2 -fold from the start of the treatment period at evaluation time point of Week 52 of the treatment period.

- The shift table for the urinary albumin/creatinine ratio (mg/g Cr), which consists of the first day of treatment and Week 52 of the treatment period, should be provided for each treatment group.

Classification follows CKD severity classification. (normal, < 30 ; microalbuminuria, ≥ 30 and < 300 ; macroalbuminuria, ≥ 300). No analysis will be performed for patient cohorts.

(14) QOL indices (EQ-5D-5L, KDQOL)

The score of the QOL index should be calculated and provided by treatment group.

EQ-5D-5L

The number, proportion, and their two-sided 95% CI (Clopper-Pearson [Exact] method) of subjects in responses in 5 levels to the 5 questions (mobility, self care, usual activities, pain/discomfort, anxiety/depression) should be provided at each evaluation time point.

For Index value and VAS score, descriptive statistics of measured values and descriptive statistics of changes from the first day of the treatment period should be provided for each treatment group at each evaluation time point. A paired t-test should be performed for before and after comparison of changes from the first day of the treatment period.

A group comparison should be conducted for the changes in Index value and VAS score from the first day of the treatment period at each evaluation time point using the MMRM (with compound symmetry [CS] for a covariance matrix within subject variance). LSMean, its standard errors, and 2-sided 95% CI should be calculated, and the point estimate, its standard errors, 2-sided 95% CI, and p-value should be provided for the group difference (MT-6548 – darbepoetin) of the LSMean by treatment group.

The correlations of Hb value and Index Value, and Hb value and VAS score at all evaluation time points should be evaluated using linear regression and Emax model. For linear regression, the estimated items analyzed by the following model (refer to “linear regression model”) should be output, and the p-value of the test with 0 slope as the null hypothesis should be calculated. Scatter plots and regression lines should be prepared separately for each treatment group. On the Emax model, estimated items (refer to “Emax model”) analyzed by the following model should be output. Scatter plots and regression curves should be prepared separately for each treatment group. No analysis will be performed for patient cohorts.

The correlation between the change in Hb from the first day of the treatment period and the change in Index Value from the first day of the treatment period and the correlation between the change in Hb from the first day of the treatment period and the change in VAS score from the first day of the treatment period should be analyzed in linear regression in the same way as the correlation between Hb value and Index Value and between Hb value and VAS score, respectively. Only the Correction and Conversion (Hb <11.0 g/dL) cohorts should be analyzed

[Linear regression model]

regression equation $Y = aX + b$

X: Hb value, or change in Hb value from the first day of the treatment period

Y: Index Value, or VAS score, or change from the first day of the treatment period on the left

Estimated items (output item): a: slope of the regression line and its standard error, b: intercept of the regression line and its standard error, r: correlation coefficient

[Emax model]

Model 4-parameter logistic model

X: Hb value

Y: Index Value or VAS score

Estimates (output item): EC₅₀ with its standard errors and 2-sided 95% CI, Emax with its standard errors and 2-sided 95% CI, min with its standard errors and 2-sided 95% CI, slope with its standard errors and 2-sided 95% CI, R-Square (contribution ratio).

KDQOL

Descriptive statistics of KDQOL should be calculated by subscale (Section 4.13 [Table 4.13.2] “subscale”) for measured values and changes from the first day of the treatment period at each evaluation time point by treatment group. Scores by subscale should be calculated using a scoring method (Section 4.13). Scores by subscale should be calculated using a scoring method (Section 4.13). A paired t-test should be performed for before and after comparison of changes in KDQOL from the first day of the treatment period.

A group comparison should be conducted for the change in KNDQOL from the first day of the treatment period at each evaluation time point using the MMRM (with compound symmetry [CS] for a covariance matrix within subject variance). The point estimate of LSMean, its standard errors, and 2-sided 95% CI should be calculated by treatment group, and the point estimate, its standard errors, 2-sided 95% CI, and p-value should be provided for the group difference (MT-6548 – darbepoetin) of the LSMean.

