16.1.9 Documentation on Statistical Methodology

Confidential

operating procedure for randomized key code table preparation and storage. Subjects who are judged eligible to enter the treatment period are assigned to treatment groups in ascending order of the randomization number based on the randomization key code table for each stratification factor, and the treatment groups assigned on the Web registration system are notified. The investigator/coinvestigator should prescribe the study drug of the treatment group notified on the Web registration system. Further details of randomization methods shall be specified in the standard operating procedure for randomization key code table preparation and storage.

Subjects should be randomly assigned in a 1:1 ratio to MT-6548 and darbepoetin groups with the following stratification factors.

- ✓ Correction cohort or Conversion cohort
- ✓ Mean Hb levels during the screening period (mean of the latest two central measurements):
 - Correction cohort: <10.0 g/dL or \geq 10.0 g/dL
 - Conversion cohort: <11.0 g/dL or \geq 11.0 g/dL

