4.11 Iron supplement dosage

The dose of iron supplements is defined by the following formula. However, the dose of iron supplements will not be calculated if iron supplements are used as needed.

Mean monthly dose of iron supplements during the screening period* and each scheduled study visit period*² (tabulation period of iron supplements) = (Daily dose based on the physician's prescription × Period of administration (days) of the corresponding dose^{*3} during the tabulation period of iron supplements)/Tabulation period of iron supplements (days)^{*4} × 30.4375^{*5}

*: The number of days of the screening period is “First day of the treatment period – First day of the screening period”.

*²: For each period between the scheduled study visits, the actual study visit dates are not considered, and this tabulation is fixed as follows:

- ✓ The first day of the treatment period to Week 2 of the treatment period: The first day of the treatment period (1 day) to 14 days.
- ✓ Week 2 of the treatment period to Week 4 of the treatment period: 15 to 28 days.
- ✓ The same should apply thereafter, and the final period between the scheduled study visits should be Week 48 to Week 52 of the treatment period: 337 days to the day before the day of blood sampling for hematological tests at Week 52 of the treatment period. However, for subjects who discontinued their treatment, the final period between the scheduled study visits should be up to the day before discontinuation.

*³: If there are multiple applicable doses, the sum of the calculated values for each dose should be used.

*⁴: For subjects who discontinued their treatment, the final period between the scheduled study visits (days) should be the actual number of days until the day before discontinuation.

*⁵: In this tabulation, 1 month is counted as 30.4375 days (365.25/12 = 30.4375).

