8.5 Efficacy analysis

As a general rule, efficacy analysis will be performed on the FAS. When necessary, descriptive statistics for continuous variables should be calculated and frequency and proportion will be calculated for discrete variables. Unless otherwise specified, a similar analysis will be conducted for patient cohort. No data from the day after the rescue therapy implementation date should be included in the efficacy analysis.

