8.5.1 Analysis of secondary endpoints

(1) Mean Hb values at Weeks 48 and 52 of the treatment period

Descriptive statistics for change from Hb on the first day of the treatment period to mean Hb at Week 48 and Week 52 in the treatment period should be calculated by treatment group. The MMRM is used to model the mean Hb values at each evaluation time point based on the following model, and the mean Hb values at Week 48 and Week 52 of the treatment period for each treatment group should be obtained, and the least squares mean (LSMean), its standard error, and 2-sided 95% CIs for the mean Hb values should be calculated, and the point estimate of the between-group difference (MT-6548 -

darbepoetin) of LSMean, its standard error, and 2-sided 95% CI should be calculated. No analysis will be performed for patient cohorts.

[MMRM Model]

- Covariate: response variable value of the first day of the treatment period
- Fixed effects: Treatment group, evaluation time point, patient cohort (Correction or Conversion cohort), interactions of evaluation time point \times treatment group, interactions of patient cohort (Correction or Conversion cohort) in evaluation time point
- Degrees of freedom adjustment: Kenward–Roger method
- Covariance matrix within subject for each subject: unstructured (type = UN; unstructured)
When it was not converged using unstructured as a covariance matrix within subject variance, the setting of the covariance matrix within subject variance will be changed in the following order, and the analysis will be carried out using the covariance matrix within subject variance converged first.
Heterogeneous Toeplitz (TOEPH) \rightarrow Heterogeneous AR (1) (ARH [1]) \rightarrow Heterogeneous CS (CSH) \rightarrow Toeplitz (TOEP) \rightarrow First-order autoregressive (AR [1]) \rightarrow Compound symmetry (CS)
- Random effects: subjects

(2) Hb values at each evaluation time point in the treatment period

1) Hb values at each evaluation time point in the treatment period

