8.5.4 Statistical analysis issues

8.5.4.1 Adjustment for covariates

In the analysis of efficacy, in order to consider the effect of the measurement value of the first day of the treatment period on the change of each measurement in the group comparison, the analysis using the MMRM should be conducted using the measurement value of the first day of the treatment period as a covariate in the general analysis.

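### Final SAP 8.5.2 (7) compares change in monthly iron dose by a t-test on change scores; an ANCOVA on screening dose and cohort would use the collected data at least as efficiently

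*SAP*

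**What the plan says.** Final SAP 8.5.2 (7) takes each subject's mean monthly iron dose in screening as baseline and forms the change from it, for each between-visit period and for the whole period to Week 52. For the between-arm comparison it states: "The changes should be compared between groups using the Student-t test". It asks for the mean difference, 95% CI, t-statistic and p-value, and names no covariate or stratum. Phase 1 SAP 8.5.3 (7) and Final SAP 8.7.1 specify the same test.

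Both candidate covariates exist. Final SAP 4.11 defines the "Mean monthly dose of iron supplements during the screening period", and 2.3 lists "Correction cohort or Conversion cohort" as a stratification factor for randomisation.

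Elsewhere the plan adjusts. On group comparisons of change, Final SAP 8.5.4.1 says "the analysis using the MMRM should be conducted using the measurement value of the first day of the treatment period as a covariate". The Hb MMRM in 8.5.1 (1) also carries a cohort term. The neighbouring iron indices and hepcidin in 8.5.2 (10) are compared by MMRM, and Phase 1 SAP 8.5.2 (4) uses ANCOVA for the Hb increase rate.

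On cohorts, Final SAP 8.5 sets the default: "Unless otherwise specified, a similar analysis will be conducted for patient cohort". Section 8.5.2 (7) does not switch this off.

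**The concern.** Iron dose is the one between-arm comparison of a continuous outcome that leaves out the baseline covariate, and no reason is given. Change is likely to depend on where a subject starts. No iron is tabulated as 0 mg, so a subject on none in screening cannot fall, while a user can. If the true slope of treatment-period dose on screening dose is not 1, part of any between-arm difference in screening dose passes into the estimated difference in change, and the interval is wider than it need be.

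At stake are the precision and stability of a reported difference, CI and p-value on how much iron each arm needed. No decision rule or sample-size argument in the plan depends on them.

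**Working it through.** **The plan's own figure.** There is none for iron dose. The only power statement (Final SAP 2.5, over 95% with 150 per arm) concerns Hb. Its non-inferiority part reproduces: SE = 1.78 × √(2/150) = 0.2055; 0.75/0.2055 − 1.96 = 1.69; power = 95.4%. It has no bearing on this comparison.

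**Inputs.** The test and the baseline definition come from Final SAP 8.5.2 (7) and 4.11. Two quantities are assumed, because the documents give neither: ρ, the correlation of screening and treatment-period dose, and k, the treatment SD divided by the screening SD.

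**Formulas** (screening SD = 1):
- Variance of a change score: 1 + k² − 2ρk.
- Residual variance after regression on screening dose: k²(1 − ρ²).
- The first minus the second is (1 − ρk)², which is never negative and is zero only when ρk = 1.
- Variance ratio, ANCOVA to t-test: k²(1 − ρ²)/(1 + k² − 2ρk). With k = 1 this is (1 + ρ)/2.
- Shift in the change-score estimate per unit of baseline difference between arms: ρk − 1.

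**Example.** With k = 1.5 and ρ = 0.5: 2.25 × 0.75 = 1.6875; 1 + 2.25 − 1.5 = 1.75; ratio 0.96. Shift: 0.75 − 1 = −0.25.

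| k | ρ | Variance ratio | CI narrower by | Shift for a 10 mg/month baseline difference |
|---|---|---|---|---|
| 1 | 0.3 | 0.65 | 19.4% | −7.0 mg |
| 1 | 0.5 | 0.75 | 13.4% | −5.0 mg |
| 1 | 0.7 | 0.85 | 7.8% | −3.0 mg |
| 1.5 | 0.3 | 0.87 | 6.7% | −5.5 mg |
| 1.5 | 0.5 | 0.96 | 1.8% | −2.5 mg |
| 1.5 | 0.7 | 1.00 | 0.1% | +0.5 mg |
| 2 | 0.3 | 0.96 | 2.1% | −4.0 mg |
| 2 | 0.5 | 1.00 | 0% | 0 mg |
| 2 | 0.7 | 0.93 | 3.7% | +4.0 mg |

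A value of k below 1 cannot be ruled out for the whole-period summary, because screening lasts at most 6 weeks and treatment up to 52. At k = 0.7 the ratios are 0.42, 0.47 and 0.49 for ρ = 0.3, 0.5 and 0.7.

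**Simulation** (no true effect, k = 1, 3,000 trials per setting, 150 or 75 per arm). Both methods were unbiased on average. Type I error was 4.4–5.5% for the t-test and 4.6–5.4% for ANCOVA. At 150 per arm and ρ = 0.3, 0.5, 0.7, the t-test estimate correlated with the chance baseline difference at −0.59, −0.52 and −0.38; for ANCOVA the correlation was near zero.

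The further gain from a cohort term cannot be calculated from the documents.

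**The case against.** The strongest reply is that nothing here is wrong. A t-test on change is unbiased under randomisation and holds its size, and its CI already allows for ordinary chance imbalance. That stands: this is a matter of efficiency and of sensitivity to imbalance.

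Four stronger readings are tempting, and the documents do not support them.
- *The analysis ignores baseline and cohort.* Subtracting the screening dose uses baseline, with a fixed slope of 1. The default in Final SAP 8.5 repeats the comparison within cohorts, so only the pooled estimate lacks a cohort term.
- *Section 8.5.4.1 is breached.* That section describes MMRM with a first-day value. Iron dose has a screening-period mean as its baseline and a test of its own. The plan departs from its general practice without contradicting itself.
- *Any baseline difference in this table is due to chance.* Section 8.5.2 (7) drops subjects who never took iron on treatment and those who changed route. Both depend on events after randomisation, so screening doses may differ between arms for other reasons. ANCOVA does not undo that selection.
- *The test should change wherever it appears.* Final SAP 8.7 re-tabulates Phase 1 iron data by the Phase 1 method to see what a data change did, and 8.5.4.3 records that the Phase 1 analysis was conducted. Changing the test there would mix a change of method with the change of data.

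The stakes are also low. Protocol 13.3.2 (3) promises only descriptive statistics for other endpoints, and Phase 1 SAP 8.5.4.7 treats them as exploratory. That limits the weight of the point, but it gives no reason to prefer the t-test.

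**Conclusion.** The point holds as a minor improvement to Final SAP 8.5.2 (7). The pooled t-test on change gives up precision that data already collected may supply, and its estimate moves by ρk − 1 per unit of baseline imbalance. For assumed ρ of 0.3–0.7 and k of 1–2, the variance ratio is 0.65 to 1.00, a CI between 0% and 19.4% narrower. The gain is larger if k is below 1 and nil if ρk = 1. In large samples the adjusted variance is not larger.

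These figures rest on assumed ρ and k and on comparing arms as randomised, which the table's exclusions weaken. The planned test is not invalid, and the Hb non-inferiority conclusion is untouched.

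**What to change.** In Final SAP 8.5.2 (7) only, make the between-arm comparison an ANCOVA: change in mean monthly iron dose on treatment, screening-period mean monthly iron dose and cohort (Correction or Conversion), with cohort omitted in the by-cohort tables. Report the adjusted difference (MT-6548 minus darbepoetin), its 95% CI and p-value. Keep the t-test as a sensitivity analysis and leave the descriptive statistics as they are. Add a sentence that adjustment does not correct for excluding never-users and route changers.

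Leave the method in Final SAP 8.7.1 and Phase 1 SAP 8.5.3 (7) unchanged, so that the re-tabulation isolates the data change.

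The cost is a few lines of SAP text and one extra model, with no new data. The headline figure becomes a model-based difference, with the raw one beside it. If the final data are already locked, Protocol 13.4 requires the reason to be recorded and the result to be distinguished from the original plan.
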